2.3. Known and Potential Benefits and Risks to Patients

2.3.1. Known and Potential Benefits and Risks of the Test Investigational Medicinal Product(s)

Olanzapine is a well characterized and commonly prescribed second-generation antipsychotic drug available as oral and im formulations. Oral formulations (Section [2.1.2.1](#)) are approved for the treatment of adults and adolescents affected by schizophrenia. The long-acting im depot preparation containing olanzapine pamoate (Section [2.1.2.2](#)) is approved for the treatment of adults affected by schizophrenia, while a rapid-acting im formulation of olanzapine

(Section 2.1.2.1) is approved for the treatment of adults with acute agitation associated with schizophrenia.

Data from Study TV44749-SAD-10154, including pharmacokinetics, safety, and tolerability associated with TV-44749, ie, olanzapine for extended-release injectable suspension (for sc use), are available. To date, the sponsor has evaluated TV-44749 safety data from 71 patients and 30 healthy subjects at doses of 70 to 566 mg and 6 healthy subjects treated with TV-44749 vehicle. The safety profile emerging from these data is consistent with that seen with other olanzapine formulations (Section 2.2.2.2), with the exception of the identification of ISRs. None of these were identified as serious events, and they have not significantly impacted TV-44749's benefit-risk profile. [REDACTED]

[REDACTED] The current ZYPREXA label contains warning language describing an association with hyperglycemia, diabetes mellitus, weight gain, and lipid elevations. The label also contains the standard boxed warning regarding increased risk of mortality in elderly patients with dementia-related psychosis.

Furthermore, it has been proposed that the rapid and significant increases in plasma concentration leading to an olanzapine overdose and PDSS with ZYPREXA RELPREVV arise from vessel injury during the im injection process. Vessel injury could result in blood contact, causing rapid dissolution due to the marked increase in solubility of olanzapine pamoate in plasma compared to the intended im environment, and ultimately lead to an olanzapine overdose (Heres et al 2014). [REDACTED]

[REDACTED]

[REDACTED]

[REDACTED]

No suspected PDSS event occurred in Study TV44749-SAD-10154.

Additional information regarding benefits and risks to patients may be found in the IB.

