- i. The patient has taken clozapine or has received electroconvulsive therapy within the last 12 months prior to screening.
- j. The patient is currently receiving daily oral olanzapine at a dose >20 mg/day.
- k. The patient has current or a history of known hypersensitivity to olanzapine or any of the excipients of TV-44749 or the oral formulation of olanzapine.
- l. The patient has treatment-resistant schizophrenia according to medical and psychiatric history, as judged by the investigator or documented failure of 2 or more antipsychotic medications (administered at the maximum tolerated dose for at least 6 weeks each). Participants who have responded to antipsychotics only when paired with clozapine are considered treatment resistant.
- m. The patient has had a significant sedation or delirium after antipsychotic treatment according to medical and psychiatric history and as judged by the investigator or suffered from delirium due to a medical condition.
- n. [Revision 1] The patient has any medical or psychiatric condition that, in the opinion of the investigator, could jeopardize study participant's safety (including in the context of local oral olanzapine label) or would compromise the patient's ability to participate in this study.
- o. The patient has known risk factors for undiagnosed/instable arrhythmia, congenital long QT, hypokalemia, hypomagnesemia, or autonomic failure (mostly with clinically significant orthostatic hypotension).
- p. The patient has any clinically significant uncontrolled medical condition (treated or untreated).
- q. Any disorder that may interfere with absorption, metabolism, or elimination of olanzapine
- r. The patient has a non-fasting glucose level of ≥200 mg/dL at screening.
- s. The patient had a change in their diabetes treatment within 4 weeks before the first injection of the IMP.
- t. The patient has serum triglycerides levels of ≥500 mg/dL.
- u. The patient has low-density lipoprotein levels of ≥190 mg/dL.
- v. The patient has a history of ketoacidosis or hyperosmolar coma.
- w. [Revision 1] The patient has alanine aminotransferase (ALT)/serum glutamic pyruvic transaminase values $\geq2 \times$ the upper limit of normal (ULN) of the performing laboratory, and aspartate aminotransferase (AST)/serum glutamic oxaloacetic transaminase values $\geq2 \times$ ULN, and total bilirubin values $\geq1.5 \times$ ULN at screening.

Isolated parameters for exclusion are as follows:

- ALT or AST $>5 \times$ ULN

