Potassium	Hematocrit	Hemoglobin
Chloride	Erythrocytes	pH
Creatinine ^a	Platelets	Specific gravity
Glucose	Leucocytes	Microscopic tests
BUN	Neutrophils	Bacteria
Total cholesterol	Lymphocytes	Erythrocytes
LDL	Eosinophils	Leucocytes
HDL	Monocytes	Crystals
Triglycerides	Basophils	Casts
Urate	Coagulation^d	
ALT	PT	
AST	INR	
LDH		
GGT		
Alkaline phosphatase		
Creatine kinase		
Bicarbonate		
Protein		
Albumin		
Bilirubin		
Direct bilirubin		
Prolactin ^b		

^a Glomerular filtration rate (to be calculated at screening only) will be calculated based on serum creatinine levels, weight, gender, and age using the Cockcroft-Gault equation.

^b At screening (prior to intake of oral olanzapine, where relevant), baseline (visit 2; week 0 [prior to IMP administration]), visit 11 (week 8 [prior to IMP administration]), visit 14 (week 20 [prior to IMP administration]), and at the EOT visit, clinical laboratory tests will also include prolactin.

^c At baseline (visit 2; week 0), visit 11 (week 8), visit 14 (week 20), visit 17 (week 32), visit 20 (week 44), and at the EOT visit, clinical laboratory tests will also include hemoglobin A1C.

^d At screening only.

ALT=alanine aminotransferase; AST=aspartate aminotransferase; BUN=blood urea nitrogen; EOT=end-of-treatment; ET=early termination; GGT=gamma-glutamyl transpeptidase; HDL=high-density lipoprotein; IMP=investigational medicinal product; INR=international normalized ratio; LDH=lactate dehydrogenase; LDL=low-density lipoprotein; PT=prothrombin time.

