10.5.6.4. Key Secondary Efficacy Analysis

10.5.6.5. Secondary Efficacy Analysis

10.5.6.6. Other Efficacy Analysis

10.6. Multiple Comparisons and Multiplicity

10.7. Safety Analysis

Safety analyses will follow the safety estimand approach using the safety analysis set.

The safety analysis will be by period with the respective randomization (for Period 1, randomization to Period 1 and for Period 2, randomization to Period 2). In addition, a safety analysis of the 2 periods together may be conducted; in this analysis, placebo patients in Period 1 will be counted as placebo, and after the randomization to Period 2, they will be assigned the actual dose in Period 2.

In case of dose adjustment, the patient may be regarded according to the randomized dose until the day of the dose adjustment, and from the first administration of the adjusted dose, the patient will be regarded according to the adjusted dose.

Safety assessments and time points are provided in [Table 1](#) and [Table 2](#).

All adverse events will be coded using the Medical Dictionary for Regulatory Activities. Each patient will be counted only once in each preferred term or system organ class category for the analyses of safety. Summaries will be presented for all adverse events (overall and by severity), adverse events related to test IMP and/or device (ie, reasonable possibility defined by the investigator as related or with missing relationship) (overall and by severity), serious adverse events, serious adverse device events, and adverse events and adverse device events causing withdrawal from the study. Summaries will be presented by treatment group and for all patients. Patient listings of serious adverse events and adverse events leading to withdrawal will be presented.

Changes in laboratory, ECG, and vital sign measurements data will be summarized descriptively. All values will be compared with predefined criteria to identify potentially clinically significant values or changes, and such values will be listed.

The use of concomitant medications will be summarized by therapeutic class using descriptive statistics.

For continuous variables, descriptive statistics (number [n], mean, standard deviation, median, minimum, and maximum) will be provided for actual values and changes from baseline to each time point. For categorical variables, patient counts and percentages will be provided.

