8.6. Clinical Laboratory Tests

Clinical laboratory tests (serum chemistry, hematology, urinalysis) are detailed in Table 9 of the study protocol. Central laboratory value and changes from baseline will be summarized.

Laboratory test results will be presented in standard international (SI) units. Listings will include all laboratory values (central and local laboratories).

Laboratory test results will be presented for Period 1 and for the integrated study periods.

Summary statistics for chemistry, hematology and urinalysis laboratory tests will be presented at time points detailed in the Schedule of Assessment Table 1 and Table 2 of the study protocol.

Laboratory values and changes from baseline to each scheduled visit will be summarized using descriptive statistics.

Shifts (below, within, and above the normal range) from baseline to each scheduled visit including "at any visit" assessment (as a separate visit) will be summarized using patient counts. Summaries of potentially clinically significant abnormal values will include all post-baseline values (including scheduled, unscheduled, and withdrawal visits). The incidence of potentially clinically significant abnormal values will be summarized for laboratory variables using descriptive statistics with the criteria specified in [Table 2](#) below.

Summaries will be presented for the While on treatment period (starting from the baseline visit in Period 1 to the EOT visit, including ET visit if conducted during this period). A separate summary will be presented for the Follow-Up period (any visit conducted after EOT visit and until the end of the study).

Table 2: Criteria for Potentially Clinically Significant Laboratory Values

Test	Criterion value
Serum chemistry	
Alanine aminotransferase (ALT)	$\geq 3x$ ULN
Aspartate aminotransferase (AST)	$\geq 3x$ ULN
Alkaline phosphatase	$\geq 3x$ ULN
Lactate dehydrogenase (LDH)	$\geq 3x$ ULN
Blood urea nitrogen (BUN)	≥ 10.71 mmol/L
Creatinine	≥ 177 μ mol/L
Uric acid	≥ 625 μ mol/L
Men	
Women	≥ 506 μ mol/L
Bilirubin (total)	$\geq 2x$ ULN
Potassium	≤ 3 mmol/L ≥ 6 mmol/L
Calcium	≤ 1.5 mmol/L ≥ 3.5 mmol/L
Hematology	
Hemoglobin	≤ 115 g/L
Men	
Women	≤ 95 g/L
White blood cell (WBC) counts	$\leq 3 \times 10^9$ /L $\geq 20 \times 10^9$ /L
Absolute neutrophil counts (ANC)	$\leq 1 \times 10^9$ /L
Platelet counts	$\leq 75 \times 10^9$ /L $\geq 700 \times 10^9$ /L

ULN=upper limit of normal range.

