8.9. Electrocardiography

A standard 12-lead ECG will be recorded at the time points detailed in Tables 1 and 2 of the study protocol. Triplicate measurements (approximately 5 minutes apart) will be performed at screening and baseline and single measurements at other in-clinic visits, as specified at the study protocol.

Electrocardiogram (ECG) findings (normal and abnormal) at screening and baseline will be summarized using descriptive statistics; the data presentation will include both eResearch Technology (the central ECG vendor) and investigator interpretation. The average of the 3 ECG screening and baseline assessments will be calculated; if more measurements are taken, the 3 last measurements taken prior to first dose administration will be used both for the average calculation and for choosing the worst result for the interpretation.

If the investigator interpretation is missing, the following derivation rule will be used:

1. If ERT interpretation is 'normal' then investigator interpretation on the same date will be derived as 'normal';
2. Otherwise investigator interpretation will not be derived.

Shifts (normal and abnormal) from baseline to overall result interpretation at each scheduled visit including "at any visit" assessment (as a separate visit) will be summarized using patient counts.

For overall result interpretation the worst post baseline finding for the patient (the abnormal finding if there are both normal and abnormal findings) will be used in the summaries.

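### SAP Table 2 sets no limits for glucose, HbA1c, triglycerides or LDL, so the incidence of marked metabolic abnormality is not prespecified; separately, SAP 8.9 fills a missing investigator ECG interpretation only when the central reading is normal

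*SAP*

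**What the plan says.** **Laboratory.** Protocol 10.7 says of laboratory, ECG and vital sign data: "All values will be compared with predefined criteria to identify potentially clinically significant values or changes, and such values will be listed". In SAP 8.6, "The incidence of potentially clinically significant abnormal values will be summarized for laboratory variables using descriptive statistics with the criteria specified in" Table 2. Its rows are ALT, AST, alkaline phosphatase, LDH, BUN, creatinine, uric acid, total bilirubin, potassium, calcium, hemoglobin, white cells, neutrophils and platelets. The only limits outside the table are for prolactin (SAP 8.6.2.4: 2x and 5x ULN).

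Glucose, total cholesterol, LDL, HDL and triglycerides are in the serum chemistry panel of Protocol Table 9. HbA1c is measured repeatedly; footnote c of that table runs to "visit 20 (week 44), and at the EOT visit, clinical laboratory tests will also include hemoglobin A1C".

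Protocol 2.3.1 notes: "The current ZYPREXA label contains warning language describing an association with hyperglycemia, diabetes mellitus, weight gain, and lipid elevations". Protocol 5.2 excludes patients on glucose ("The patient has a non-fasting glucose level of ≥200 mg/dL at screening"), on triglycerides ≥500 mg/dL and on LDL ≥190 mg/dL.

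**ECG.** Under SAP 8.9, if the investigator interpretation is missing and the central interpretation on that date is normal, the investigator interpretation is set to normal. For any other central result: "Otherwise investigator interpretation will not be derived". Both readers are presented at screening and baseline. Shifts from baseline are then tabulated by patient counts, using the worst finding, without saying whose interpretation is used.

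**The concern.** The SAP prevails over the protocol where they differ, so Table 2 in effect narrows the protocol's commitment on all values. SAP 17, which lists changes from the protocol, does not record the narrowing. Uric acid and LDH get an incidence of marked abnormality, while the laboratory risks named for olanzapine do not.

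The omission carries into a second analysis. SAP 8.1 repeats adverse events, serious adverse events, exposure and potentially clinically significant measures after excluding patients with a dose adjustment. Laboratory shifts are not on that list, so that analysis would hold no laboratory summary of glucose, HbA1c or lipids.

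Every value is listed, so counts could be made later. The limits would then be chosen with the data in view.

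The ECG rule raises a different problem. It adds normals to the investigator-based data and leaves centrally abnormal ECGs as gaps. That can lower a reported abnormal share and can also misclassify a patient's baseline status.

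**Working it through.** The plan states no figure to reproduce on this point. Three checks apply.

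**1. Coverage of Table 2.** Protocol Table 9 has 25 serum chemistry rows and 11 hematology rows, 36 in all (coagulation and urinalysis set aside). SAP Table 2 covers 14 of them, leaving 36 − 14 = 22 without a limit. The 22 include glucose, HbA1c, total cholesterol, LDL, HDL and triglycerides. Prolactin is also among them but gets its limits in SAP 8.6.2.4. No comparable addition is made for glucose, HbA1c or lipids.

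**2. The protocol's entry limits in SI units** (SAP 8.6 reports in SI; the divisors are the usual mg/dL-to-mmol/L factors):
- glucose: 200 / 18.02 = 11.1 mmol/L
- triglycerides: 500 / 88.57 = 5.65 mmol/L
- LDL: 190 / 38.67 = 4.91 mmol/L

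The glucose limit is explicitly non-fasting. Protocol 6.6.2 requires fasting before baseline, week 8 and EOT (preferably ET too), but chemistry is also drawn at other visits, such as weeks 4 and 20. Samples of both kinds would therefore meet the same limit.

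**3. ECG rule.** Let a be the share of ECGs that are centrally abnormal and m the share with no investigator interpretation. Assume m is unrelated to the result and that the two readers agree. The documents give neither a nor m. Among non-missing interpretations after the SAP fill, the abnormal share is

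a(1 − m) / (1 − a·m).

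Per 100 ECGs with a = 20% and m = 10%, there are 18 interpreted abnormal, 72 interpreted normal, 8 filled as normal and 2 left missing:
- SAP rule: 18 / 98 = 18.4%
- no fill at all: 18 / 90 = 20%
- fill in both directions: 20 / 100 = 20%
- all ECGs as denominator: 18 / 100 = 18%, with or without the SAP fill

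| m (a = 20%) | Share under SAP rule | Shortfall (points) |
|---|---|---|
| 0 | 20.0% | 0 |
| 5% | 19.2% | 0.8 |
| 10% | 18.4% | 1.6 |
| 20% | 16.7% | 3.3 |
| 30% | 14.9% | 5.1 |

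For a from 10% to 40% and m from 5% to 20%, the shortfall runs from 0.5 to 5.2 points.

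*Baseline.* SAP 8.9 takes the worst of three baseline ECGs. If the one abnormal replicate lacks an investigator interpretation, it stays missing, the other two read normal, and the patient is classed normal at baseline. A later abnormal ECG then counts as a new shift. The effect on shift counts can therefore go either way.

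**The case against.** **Laboratory.** The metabolic analytes are not unreported. SAP 8.6 gives means, changes and below/within/above-normal shifts with no analyte excluded, including an at-any-visit row that uses unscheduled visits (SAP 4.4). A result the investigator judges clinically significant becomes an adverse event (Protocol 8.4), tabulated by arm and severity. Weight has its own categories, with cuts at 0, 7% and 10% (SAP 8.7). Adverse events of special interest, the metabolic syndrome definition and the exploratory endpoints are redacted and may add coverage. All of this stands. It rules out the inference that the plan misses olanzapine's metabolic risks or cannot report them. It does not supply the absent item: a normal-range shift puts a barely raised value and a marked one in the same cell, and adverse event reporting depends on judgment.

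A reader might also take glucose and lipid changes to be the expected dose-related harm. Protocol 2.2.2.2 reports dose-group differences for fatigue, dizziness, weight gain and prolactin, not for glucose or lipids.

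Entry limits are not safety limits, and the glucose one is non-fasting. That is fair, so they should be labelled as tabulation limits and the fasting state shown.

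**ECG.** The rule concerns a missing investigator interpretation, not a missing ECG. It removes no abnormal finding. Protocol 8.7 requires the investigator to judge every out-of-range ECG, so interpretations may be missing mainly for normal ECGs. If only those are missing, the rule is right: with 8 of 80 normals missing and filled, the share is 20 / 100 = 20%. An abnormal ECG also needs a clinical-significance judgment that the central reading cannot give. These points limit the size, but none justifies a one-sided fill with no named reader.

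**Conclusion.** The point holds in a limited form. Table 2 has no criterion for glucose, HbA1c, triglycerides or LDL, contrary to Protocol 10.7. The incidence of marked abnormality per arm is therefore not prespecified for laboratory risks that the protocol itself names. The finding concerns one type of table, not metabolic monitoring as a whole, and has no bearing on the efficacy result. Redacted sections could contain further metabolic summaries, and that cannot be judged here.

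The ECG rule is one-sided. Where investigator interpretations are missing for centrally abnormal ECGs, the abnormal share among non-missing interpretations is too low. The percentages above are illustrations resting on assumed prevalence, missingness unrelated to result, and reader agreement. The true size is unknown and is zero if no interpretation is missing. With an all-ECG denominator the fill itself changes no abnormal count; the shortfall there comes from not carrying over central abnormals. A reader might infer that abnormal shifts are systematically understated. The documents do not support that, because the SAP does not say that the shift table uses the investigator's reading and baseline misclassification can add apparent shifts.

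**What to change.** Before Period 1 is unblinded:

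1. Add four rows to SAP Table 2, marked as tabulation limits rather than clinical thresholds: glucose ≥11.1 mmol/L, triglycerides ≥5.65 mmol/L, LDL ≥4.91 mmol/L, and HbA1c at a limit the sponsor fixes in advance (the documents offer none).
2. Count patients who did not meet the limit at baseline. Identify fasting and non-fasting samples for glucose; the same split would serve triglycerides.
3. In SAP 8.9, carry the central reading over in both directions when the investigator interpretation is missing, or base the shift table on the central reading at every visit. Name the reader and the denominator, and report how many interpretations were derived.
4. Record the changes in SAP 17.

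The cost is four table rows, one derivation line and a few more flagged values to list. All the data are already collected. If Period 1 has been unblinded, SAP 2.6.2 already requires such additions to be disclosed in the study report. The three converted limits would still predate the results; an HbA1c limit would not.

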8.6.1. Laboratory Values Meeting Hy's Law Criteria

All occurrences of possible drug induced liver injury that meet Hy's law criteria, defined as **all** of the below, will be reported as a serious adverse event:

- ALT or AST increase of $>3x$ the ULN
- total bilirubin increase of $>2x$ ULN
- absence of initial findings of cholestasis (ie, no substantial increase of alkaline phosphatase)

All incidences will be listed.

8.6.2. Other Clinical Laboratory Tests

8.6.2.1. Virology and Thyroid Screening Tests

At the timepoints defined in Table 1 and Table 2 of the study protocol, patients will be tested for HIV, hepatitis B surface antigen and hepatitis C antibody, thyroid stimulating hormone (TSH), triiodothyronine (T₃) and thyroxine (T₄). Virology is only performed at screening. Thyroid tests will be performed at screening and at the pre-defined time points due to potential effects on clinical psychiatric symptoms.

The data will be presented as listings.

8.6.2.2. Human Chorionic Gonadotropin and Follicle-Stimulating Hormone Tests

A serum β-HCG test will be performed for all women of childbearing potential at screening and the FU visit (see Table 1 and Table 2 of the study protocol). Urine β-HCG (dipstick) test will be performed for women of childbearing potential at all visits where study drug is administered (prior to study drug administration) and at the ET and EOT visits.

A FSH test will be performed at the screening visit for any female who has been without menses for at least 12 months to confirm post-menopausal status.

Note: Urine β-HCG (dipstick) test will not be performed for Both Postmenopausal women (no menses for at least 12 months [without an alternative medical cause] prior to screening and with follicle-stimulating hormone (FSH) concentration above 35 U/L) and women who are sterile (documented hysterectomy, bilateral oophorectomy, or bilateral salpingectomy or congenitally sterile).

The FSH, serum and urine β-HCG data will be listed.

